## **Methods**

**Study Design:** Prospective diagnostic clinical trial of comparative effectiveness of screening and diagnostic tools for sleep apnea.

**Study population and selection criteria:** Potential participants were consecutive patients enrolled in the TBI Model Systems (TBIMS) at six sites (Tampa FL, Seattle WA, Dallas TX, Columbus OH, Denver CO, and Philadelphia, PA) described earlier and over 19 months. Study inclusion/exclusion criteria for the TBI Model Systems and this trial are described in Table 1.63 The requirement of TBIMS enrollment at time of consent for the clinical trial was relaxed at study-month 11 to allow for earlier enrollment during rehabilitation but the clinical criteria remained unchanged.

**Recruitment Methods:** All participating sites received institutional review board approval for conduct of the study. Consecutive admissions were screened for eligibility. Participants who passed the first level of

screening (or their proxies) were consented and further screened for final eligibility including 1)  $\geq 2$  hours sleep/night based on actigraphy placement or nursing logs/report, and 2) medical stability (including no emergent medical issues precluding overnight PSG and minimal to no post-traumatic agitation, as assessed by the Agitated Behavior Scale). Once determined eligible, an overnight PSG study was conducted by a registered polysomnographic technician (RPSGT) in the participant's own bed. Within 72 hours of the PSG, questionnaire-based sleep apnea screening measures were completed with the participant and/or best source available using established TBIMS procedures by local staff blinded to PSG results. Sleep-related information during hospitalization was collected from the medical staff (snoring status, daytime sleepiness) or medical record (weight, height). The patient-reported outcome was the primary source of data. When data were missing due to the participant's inability to respond or with unknown responses, it was imputed using best source data if available otherwise was considered missing data.

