(Aim 2: Hypothesis 2.1): *Level 3 portable polysomnography with greater consumer accessibility will be equivalent (non-inferior) to the less accessible Level 1 polysomnography in determining presence of sleep apnea in TBI patients undergoing inpatient rehabilitation.* Justification of Assumptions/Power Estimate: To test hypothesis 2.1, the sensitivity (SE) and specificity (SP) of Level 3 PSG (compared to Level 1 PSG, the reference gold standard) will each be estimated and compared to fixed hypothesized rates of SE and SP considered sufficiently large enough to potentially obviate the need for Level 1 PSG. Based on a review of the literature and consensus among the investigators in this study, SE and SP no worse (non-inferior) to 90% and 60%, respectively, are considered sufficiently large enough. To test for non-inferiority of the SE to 90% and the SP to 60%, a non-inferiority threshold of $\Delta = 0.1$ is assumed for both measures. A sample size of at least 83 patients is necessary to achieve a minimum of 80% power to test the non-inferiority of the SE to 90% (assuming $\Delta = 0.1$ and $\alpha = 0.05$). A sample size of at least 153 patients is necessary for a minimum of 80% power to test the non-inferiority of the SP to 60% (assuming $\Delta = 0.1$ and $\alpha = 0.05$). Thus, a total of 153 subjects is required to sufficiently power both non-inferiority hypotheses. Analytic Plan: To test hypothesis 2.1, the sensitivity (SE) and specificity (SP) of Level 3 PSG (compared to Level 1 PSG, the reference gold standard) will each be estimated and compared to fixed hypothesized rates of SE and SP of 90% and 60%, respectively, considered sufficiently large enough. Level 1 PSG (reference) diagnosis of sleep apnea will be made based on $AHI \geq 5$. Level 3 PSG (test) diagnosis will be made based $AHI \geq 5$. A cross-tabulation of Level 3 PSG (positive/negative) versus Level 1 PSG (positive/negative) will be constructed and standard measures of diagnostic accuracy will be estimated along with 95% confidence intervals (i.e., sensitivity, specificity, positive and negative predictive values, and diagnostic accuracy). To test for non-inferiority of the SE to 90% and the SP to 60%, a non-inferiority threshold of 0.1 is assumed. If the lower bound on the 95% confidence interval for SE is strictly above 80% and the lower bound on the confidence interval for SP is strictly above 50% then non-inferiority of Level 3 PSG (compared to Level 3 PSG) can be established. All analyses will be performed using SAS v.9.4 (SAS Institute Inc., Cary, NC).

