
Exploratory Aim 1 (HTE analyses): While an analysis of heterogeneity of treatment effects does not apply to the current study design, an important question to answer is whether the diagnosis of sleep apnea can be impacted by the presence of post-traumatic amnesia (PTA). The confusion and behavioral dysregulation associated with PTA could potentially reduce the person's ability to tolerate the procedures. While the lead site has successfully obtained PSG with EEG with persons experiencing PTA, this was a single site study with a select subject population (veterans who primarily experienced blast-induced TBI). The current study will allow for an assessment of differences in diagnostic accuracy with persons who are currently experiencing PTA in comparison to those who have cleared PTA. PTA will be operationalized based on the criterion used by the TBIMS consortium (obtaining an Orientation Log or

Galveston Orientation Amnesia Test scores in target range or consistent, repeated demonstration of orientation in medical record review). Analytical Plan: To address exploratory aim 1 regarding the heterogeneity of the screening and diagnostic accuracy across relevant sub-groups, the methods detailed for the primary aims will be replicated for the subgroups of injury severity (GCS), cognitive status (PTA), motor confounds (spasticity and hemiparesis), and limb placement. As these are exploratory aims and the study is not powered to test for differences or non-inferiority within each sub-group, focus will be on comparing the effect size of proportions (Cohen's h) among the subgroups. Values for h of 0.2, 0.5, and 0.8 are typically considered to be small, medium, and large differences, respectively. All analyses will be performed using SAS v.9.4 (SAS Institute Inc., Cary, NC).

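### Exploratory Aim 1 compares unadjusted accuracy proportions between subgroups and does not limit Cohen's h to sensitivity and specificity, so a case-mix difference could be read as an effect of PTA or injury severity

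*SAP*

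**What the plan says.** In the SAP, Exploratory Aim 1 (HTE analyses) sets the question as "whether the diagnosis of sleep apnea can be impacted by the presence of post-traumatic amnesia (PTA"). The analytical plan answers it by repetition: "the methods detailed for the primary aims will be replicated for the subgroups of injury severity (GCS), cognitive status (PTA"), motor confounds and limb placement. It adds that "focus will be on comparing the effect size of proportions (Cohen's h) among the subgroups", and gives a scale for reading the result: "Values for h of 0.2, 0.5, and 0.8 are typically considered to be small, medium, and large differences, respectively". It also concedes that "the study is not powered to test for differences or non-inferiority within each sub-group".

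The methods to be repeated are those of the two primary aims. For Aim 2 the SAP says that "standard measures of diagnostic accuracy will be estimated along with 95% confidence intervals (i.e., sensitivity, specificity, positive and negative predictive values, and diagnostic accuracy"). The Aim 1 analytic plan lists the same five measures plus ROC curves and AUC. Both aims define apnea as Level 1 AHI of at least 5.

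Exploratory Aim 1 does not say which of these proportions enter h. It names no adjustment, stratification or standardisation for prevalence or AHI severity. The SAP's one rule on group differences, under missing data, concerns drop-outs versus completers. The protocol's Statistical Analysis Plan section adds that the Aim 2 analyses were run at AHI cut-offs of 5, 15 and 30, overall and by subgroup.

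**The concern.** The question is whether PTA changes how well a test works. The planned statistic mixes that with who is in each subgroup, by two routes.

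- **Prevalence.** PPV, NPV and overall accuracy depend on how common apnea is in the subgroup. They can differ between PTA and cleared patients when the test behaves identically in both.
- **Severity mix.** Everyone with AHI of at least 5 counts as positive. Patients close to 5 are the easiest to misclassify, so a subgroup with more borderline cases can show lower sensitivity with no change in the device. The same holds for specificity among those just below 5.

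The SAP supplies labels of small, medium and large for h. A reader who applies them to an unadjusted PPV or accuracy difference could report a PTA effect that is only case mix, or miss a real effect that case mix offsets.

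**Working it through.** Exploratory Aim 1 states no sample size or effect estimate, so there is no figure of its own to reproduce. The check asks how large h can be when the test works equally well in both subgroups.

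**Inputs from the documents.** Sensitivity (SE) 0.90 and specificity (SP) 0.60 (SAP, Aim 2); design prevalence 30% and published prevalence 37-39% (SAP, Aim 1); 214 patients for Aim 2 (study summary). No prevalence or severity by subgroup is given, so every between-subgroup contrast below is an assumption.

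**Formulas** (p = prevalence).
- PPV = p·SE / [p·SE + (1−p)(1−SP)]
- NPV = (1−p)·SP / [(1−p)·SP + p(1−SE)]
- Accuracy = p·SE + (1−p)·SP
- h = 2·arcsin√p₁ − 2·arcsin√p₂, quoted below in absolute value

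**Step 1: prevalence only, SE and SP identical, 25% versus 50%.**
- PPV: 0.225/(0.225+0.300) = 0.429 versus 0.450/(0.450+0.200) = 0.692; h = 0.54.
- NPV: 0.450/(0.450+0.025) = 0.947 versus 0.300/(0.300+0.050) = 0.857; h = 0.31.
- Accuracy: 0.225+0.450 = 0.675 versus 0.450+0.300 = 0.750; h = 0.17.
- SE and SP: unchanged, h = 0.

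**Step 2: other prevalence contrasts.**

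| Prevalence | h, PPV | h, NPV | h, accuracy |
|---|---|---|---|
| 37% vs 39% | 0.04 | 0.02 | 0.01 |
| 30% vs 39% | 0.199 | 0.11 | 0.06 |
| 30% vs 50% | 0.41 | 0.25 | 0.13 |
| 25% vs 50% | 0.54 | 0.31 | 0.17 |

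**Step 3: severity mix, effect on SE and SP.** Assume log AHI is normal with SD 1.2, the mean is set to give the stated prevalence at the cut-off of 5, and Level 3 error is identical in both subgroups (log SD 0.4 to 0.8, bias 0 or −0.2).
- 30% versus 60%: SE differs by 4.7 to 7.8 points (h 0.15 to 0.196) and SP by 2.5 to 6.5 points (h 0.12 to 0.17).
- 30% versus 39%: h is about 0.04 to 0.06 for both.

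A cruder model sets the SE of each severity stratum directly and keeps it equal in both subgroups. With mild SE 0.50 to 0.85, moderate-or-worse SE 0.90 to 1.00, and mild shares from 60%/40% to 80%/20%, h for SE runs from 0.08 to 0.53. The top of that range needs the extreme 80%/20% mix.

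**Step 4: sampling error.** The 95% half-width of h is 1.96·√(1/n₁+1/n₂). At 30% prevalence, 214 × 0.30 = 64 positives, or 32 per subgroup with an even split. For SE this gives 1.96·√(2/32) = 0.49.

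For PPV the denominators are the test positives. With 107 patients per subgroup at 25% and 50% prevalence, these are 107 × 0.525 = 56 and 107 × 0.65 = 70, so the half-width is about 0.35. The PPV artefact of 0.54 exceeds it. For NPV the counts are 107 × 0.475 = 51 and 107 × 0.35 = 37, with a half-width of about 0.42, and the artefact of 0.31 lies inside it.

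**The case against.** The other side has a good case on several points.

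- **The primary quantities are SE and SP.** The Aim 1 tests compare paired sensitivities and specificities, and the Aim 2 criterion is joint on the two. Prevalence alone moves neither. This stands. But the plan repeats PPV, NPV and accuracy as well, and nothing in Exploratory Aim 1 confines h to SE and SP.
- **The SE and SP artefact is small.** Under the simulation it stays below the SAP's lowest benchmark, and a half-width near 0.49 for SE swamps it. This stands. The prevalence route is the stronger part of the point.
- **The aim is exploratory, unpowered and carries no causal claim.** This limits what is at stake. It excuses imprecision, but not a measure that differs when the tests do not.
- **Severity is not ignored.** The protocol's three AHI cut-offs by subgroup are a partial answer for Aim 2. They move the threshold but do not equalise the AHI distribution on either side of it.

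Three stronger readings are tempting and unsupported. A reader might infer that PTA patients do have different prevalence or severity; no figure by PTA status is given. A reader might take 30% and 39% as a subgroup range; 30% is a conservative whole-sample design value and 37-39% comes from published reports. A reader might tie PTA status to enrolment period, because the TBIMS-enrolment requirement "was relaxed at study-month 11 to allow for earlier enrollment during rehabilitation". The protocol says that the clinical criteria did not change, and final eligibility still required medical stability and little or no agitation. Earlier enrolment is not shown to mean more testing during PTA.

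**Conclusion.** The point holds in a limited form. As written, Exploratory Aim 1 can show a subgroup difference in PPV, NPV or accuracy when the test performs equally in both groups. At an assumed 25% versus 50% prevalence the PPV difference passes the SAP's medium benchmark and the NPV difference its small one; accuracy stays below small. At 30% versus 39% the PPV value is 0.199, just under small, and at 37% versus 39% it is negligible. The size therefore rests on a prevalence contrast that the documents neither give nor rule out.

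For SE and SP the severity artefact is below 0.2 under the log-normal assumptions, and larger only under more extreme assumed mixes. The conclusion is that a case-mix difference could be read as a PTA or GCS effect, not that it will be. No primary conclusion depends on this. It should be corrected because the remedy is specific and uses data already collected.

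**What to change.** Amend the analytical plan of Exploratory Aim 1 in the SAP, or report the following as a supplementary analysis if results are already out:

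1. Compute subgroup h for SE and SP only, with confidence intervals. Give subgroup PPV and NPV at one common prevalence, that of the whole sample.
2. Report the Level 1 AHI distribution in each subgroup.
3. For Level 3, compare the paired Level 3 minus Level 1 AHI difference by PTA status, accounting for Level 1 AHI. Make this the main check on whether PTA degrades the test: it uses every patient with both recordings, not only those misclassified.
4. Describe remaining differences as associations.

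A regression of misclassification on PTA, AHI and enrolment period is not recommended. Nor is a rule that credits PTA only if a difference survives such a model. At 30% prevalence and SE 0.90, about 64 × 0.10 = 6 Level 3 misses are expected, too few for three terms, and the rule would tend to hide a real effect.

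The cost is SAP wording and a few exploratory analyses, with no new data. The results will remain imprecise in small subgroups.
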